1.1 PROTOCOL SUMMARY

In patients undergoing hemodialysis for the treatment of end-stage renal disease, Venous Needle Dislodgement (VND) is a rare, but potentially fatal situation in which the needle delivering a patient's blood back to the body after filtration by a dialysis machine becomes inadvertently disconnected from the patient. Hemotek Medical Inc. has developed the V Needle, a venous needle return that is designed to reduce patient risk from exsanguination-related injury or death. This clinical study will serve as a confirmatory study to gain FDA marketing clearance of the Hemotek V Needle system in the clinical setting. During this study, we will determine the ability of the V Needle to successfully deliver appropriate hemodialysis therapy per the facility's guidelines. It will also be used to determine if the V Needle triggers false blood alarms under normal operating conditions. This study will also be used to demonstrate the V Needle meets effective usability criteria. Rates of adverse events and ability to complete the hemodialysis session will be compared to the rates recorded using commercially available devices during the hemodialysis sessions prior to the use of the Hemotek V Needle.

This study is a prospective, multi-center, single-arm study with subjects acting as their own control designed to confirm the safety, performance, and usability of the V Needle, a new safety needle for use during in-clinic hemodialysis that is designed to automatically generate a partial occlusion of the internal fluid path and trigger the hemodialysis machine to alarm and shut off if a complete dislodgement of the venous needle from the arm inadvertently occurs.

The study is an open-label, non-randomized, single arm, multi-center trial with subject's serving as their own control. For the first three (3) control sessions, subjects will undergo usual hemodialysis sessions with a commercially available device. For the remaining six (6) sessions, subjects will be cannulated with a V Needle in place of a usual venous line AV fistula set.

The hemodialysis sessions will be conducted in the clinic. Subjects will be observed by a clinician for the duration of each session. Clinicians will monitor the session for any abnormal disruptions, therapy interruptions, and/or adverse events, including hemolysis, due to V Needle presence. All machine blood alarms, therapy interruptions, and/or partial or complete needle dislodgements will be recorded and immediately corrected. A clinician will perform cannulation.

Cannulation site and surrounding tissue will be examined by the nurse and assessed for any locally induced trauma before and after treatment.

A survey will be completed by the clinicians and patients to assess usability, comfort, and feelings of safety of the V Needle.

After the first five (5) patients will be enrolled, and data through the last visit of the fifth patient is available, this data will be submitted to the FDA while study enrollment and visits continue. No Hemotek Medical V Needle treatments will occur until after FDA has reviewed the data from the first 5 patients and allows the study to proceed. Data will also be submitted to the FDA after the tenth patient completes their last visit and data is available. After the tenth patient, study Hemotek Medical Inc.

Confidential

enrollment and visits can continue, but no Hemotek Medical V Needle treatments will occur on the final 5-10 patients until the FDA allows the study to proceed. After FDA has found the data for the first 10 patients acceptable, the rest of the study can continue until the end.

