1.7 STUDY DEVICE

The Hemotek V Needle A.V. Fistula Set is a set that includes a needle used to access the vasculature during hemodialysis. The V Needle incorporates both a detection system that is designed to detect when the venous needle becomes completely dislodged from the patient's arm

Hemotek Medical Inc. Confidential

and an internal mechanism that is designed to occlude the flow of blood through the needle in the dislodged state. The induced flow occlusion is designed to generate a change in the venous line pressure such that the hemodialysis machine will automatically alarm and halt further pumping. The V Needle used in this study will have a sharp cannula tip with an anti-stick needle guard.

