1.8 STUDY RATIONALE

In patients undergoing hemodialysis for the treatment of end-stage renal disease, Venous Needle Dislodgement (VND) is a rare, but potentially fatal situation in which the needle delivering a patient's blood back to the body after filtration by a dialysis machine becomes inadvertently disconnected from the patient. The use of the V Needle as a venous needle return is designed to significantly reduce patient risk from exsanguination-related injury or death. This clinical study will serve to confirm safety, performance, and usability of the device during appropriate hemodialysis therapy. During this study, the safety and performance of the V Needle during delivery of appropriate hemodialysis therapy will be tested. The study will also assess the number of false blood alarms observed under normal operating conditions and the V Needle's usability. V Needle rates of adverse events and ability to complete the hemodialysis session will be compared to the rates recorded using standard available needle sets during hemodialysis sessions prior to the use of the Hemotek V Needle.

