1.23 SCHEDULE OF ACTIVITIES (SOA)

Table 1: Schedule of Activities

	Enrollment Visit	Control Dialysis Sessions (Visit 1-3)	Test Dialysis Sessions (Visit 4-9)	Final Study Visit (7-10 days after Visit 9)
Informed Consent	X			
Inclusion/Exclusion	X			
Demographics	X			
Medical History Form	X			
Vital Signs	X			
Adverse Event Form	X	X	X	X
Therapy Assessment Form, including the following: 
• Treatment success/failure• Blood alarms• Flow rates• Prescribed treatment time• Achieved treatment time• Prescribed blood flow rate• Achieved blood flow rate• Ability to cannulate fistula		X	X	
Patient Survey			X	
Clinician Survey		X	X	

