9.1.2 Control Dialysis Sessions

The assessment of the ability to successfully complete the session will be determined by the clinician and recorded on the Therapy Assessment Case Report Form (CRF). The actual treatment time will also be recorded. Adverse events will be recorded on an Adverse Event Case Report Form. Photos of the cannulation may be taken.

Additional performance measures include the following:

- Machine alarm rate (blood alarms only) during hemodialysis therapy, including false alarms and relationship of alarm to venous needle
- Changes to blood flow rate setting during therapy sessions and relationship to venous needle
- Venous, transmembrane, and/or arterial pressure measurements
- Clinician survey, evaluating the following items:
 - use of the device according to the instructions for use (IFU)
 - ability to properly cannulate
 - ability to objectively see flashback
- Achieved treatment time
- Achieved blood flow rate
- Ability to cannulate fistula
- Episodes of partial or complete needle dislodgment

In the event that the venous needle becomes 1) completely dislodged, or 2) partially dislodged and the venous pressure increases by more than 40 mm Hg indicating some disruption of the fluid flow, the event should be recorded on the therapy assessment and AE CRFs and appropriate laboratory tests (including CBC, plasma hemoglobin concentration, serum electrolytes) shall be obtained.

Patients shall be monitored for symptoms of hemolysis; if hemolysis is suspected, an AE form should be completed and appropriate laboratory tests (including CBC, plasma hemoglobin concentration, serum electrolytes) shall be obtained.

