10.3.4 Alarm categories and definitions

The following definitions are used for dialysis machine alarms:

True Alarm: Alarm was appropriate because clinician action was required beyond resetting the alarm (e.g., venous needle dislodgement, significant needle movement, infiltration, tape failure), and/or V Needle footplate opened appropriately.

False Alarm: No clinician action was required beyond resetting the alarm, and/or V Needle footplate opened inappropriately.

The following definitions will be used for the footplate opening:

Appropriate footplate opening: Footplate opening due to a VND or infiltration and/or needle movement, tape failure, or other condition that can potentially lead to a VND or infiltration.

Inappropriate footplate opening: Footplate opening that is not due to a VND or infiltration and/or needle movement, tape failure, or other condition that can potentially lead to a VND or infiltration

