10.4 Other Statistical Considerations

10.4.1 General/Summary Metrics

Simple descriptive statistics will be displayed for all relevant variables collected under the study, and be presented on the session-level (between-subject), with the exception of the additional analysis of the primary performance measure which will be done on the individual-level (within-subject).

Continuous variables will display number of observations/counts measured, mean, standard deviation, median, min/max, Q1/Q3, and 95% confidence intervals where appropriate; categorical variables will display frequency counts and percentages.

These variables will include but are not limited to the following:

- Subject demographics (including age, gender, weight, height, etc.)
- Medical history characteristics (including concomitant medication, duration in which subject was diagnosed with renal disease, any concurrent ailments, etc.)

Unless otherwise specified, all p-values will be considered significant at $\alpha=0.05$ if tests are two-sided and $\alpha=0.025$ if tests are one-sided.

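### The false-alarm aim has no prespecified V Needle versus control contrast, interval or rate denominator, although the data for one are collected under both needles

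*Combined protocol and SAP*

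**What the plan says.** The aim appears in 1.1 and again in 3.1: "It will also be used to determine if the V Needle triggers false blood alarms under normal operating conditions". Section 1.8 is softer: "The study will also assess the number of false blood alarms observed under normal operating conditions and the V Needle's usability". Section 3.3.1 puts needle malfunction leading to machine false alarms first among the risks specific to the V Needle.

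The measure is listed for control sessions (9.1.2) as "Machine alarm rate (blood alarms only) during hemodialysis therapy, including false alarms and relationship of alarm to venous needle", and in the same words for test sessions (9.1.3). The schedule in 1.23 puts blood alarms and achieved treatment time on the Therapy Assessment Form at all 3 control and 6 test sessions.

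Section 10.3.4 defines true and false alarms, for example "False Alarm: No clinician action was required beyond resetting the alarm, and/or V Needle footplate opened inappropriately". It contains definitions only. The rest of 10.3 gives tests for session success, confidence bounds for adverse events and a rank test for survey scores. Alarms therefore fall under 10.4.1, where variables are to be "presented on the session-level (between-subject), with the exception of the additional analysis of the primary performance measure". The comparisons with control promised in 1.1 and 1.8 are for adverse events and session completion.

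**The concern.** A false alarm can occur with any venous needle, and the study records alarms in control sessions too. Whether the V Needle triggers false alarms is therefore a question about excess over each subject's background, and the plan estimates no excess. Readers would have two separate summaries, an alarm rate whose denominator is not stated, and no rule for comparing them.

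Two features of 10.4.1 make this worse. Each subject serves as his or her own control, but within-subject analysis is reserved for the primary performance measure. Each subject also contributes up to six V Needle sessions, and a session-level interval treats these as independent. In a confirmatory study meant to support clearance, a statement about false alarms would then rest on an analysis chosen after the data are seen.

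**Working it through.** **Plan's own figure.** None exists for alarms. The stated 87 test sessions and 85% power concern session success. Exact enumeration of the Farrington-Manning test gives 85.5% at 87/44 sessions, so that figure reproduces, but it says nothing about alarms.

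**Step 1: collected against analysed.**

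| Element needed | Collected? | Used for alarms in 10.3 or 10.4.1? |
|---|---|---|
| Alarms under both needles | Yes (1.23, 9.1.2, 9.1.3) | Summarised by session only |
| True/false status, relation to venous needle | Yes (9.1.2, 9.1.3, 10.3.4) | No contrast |
| Achieved treatment time | Yes (1.23) | Not tied to alarms |
| Pairing within subject | Yes, by design (5.1) | Not used |
| Interval for V Needle minus control | Computable | Not specified |

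**Step 2: effect of ignoring repeat sessions.** Assumptions (not in the documents): alarm counts per session are Poisson with mean μ, multiplied by a subject effect with mean 1 and variance v. Two sessions of one subject then have correlation ρ = vμ/(1 + vμ). With 6 sessions per subject the variance of the V Needle mean is inflated by DE = 1 + 5ρ, and a nominal 95% session-level interval covers about 2Φ(1.96/√DE) − 1.

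| μ | v | ρ | DE | Coverage |
|---|---|---|---|---|
| any | 0 | 0 | 1 | 95% |
| 0.3 | 0.5 | 0.15/1.15 = 0.13 | 1.65 | 87% |
| 0.3 | 1 | 0.3/1.3 = 0.23 | 2.15 | 82% |
| 0.6 | 1 | 0.6/1.6 = 0.375 | 2.875 | 75% |
| 2.0 | 1 | 2/3 = 0.67 | 4.33 | 65% |

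Simulation with 18 subjects gives about 62-86% for v between 0.5 and 1. This agrees with the formula, and is slightly lower because the counts are skewed. A paired interval based on 18 subject differences shows a false excess in about 3-4% of trials, against a nominal 2.5%.

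**Step 3: precision of a comparison.** Section 10.3.1 expects 108 test and 54 control sessions. At about 3 hours each (1.12) that is 324 and 162 hours. Let p be the share of sessions with at least one false alarm (assumed, equal under both needles). With sessions treated as independent, the 95% half-width for the difference is 1.96·√[p(1−p)(1/108 + 1/54)]:

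- p = 5%: 1.96·√(0.0475 × 0.02778) = 7.1 points
- p = 10%: 9.8 points
- p = 20%: 13.1 points
- p = 30%: 1.96·√(0.21 × 0.02778) = 15.0 points

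At the 87-session minimum with 44 control sessions, the range is 7.9 to 16.6 points. Pairing multiplies the variance by (1 − ρ). At p = 10% the 108/54 half-width falls from 9.8 to 9.3 points (ρ = 0.1) or 8.2 points (ρ = 0.3). With 108/54 independent sessions and 80% power, the smallest detectable V Needle shares are 21%, 29%, 42% and 53% for control shares of 5%, 10%, 20% and 30%.

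**Step 4: does pairing buy power?** With 18 subjects, v from 0 to 1 and alarms doubling from 0.3 to 0.6 per session, a paired interval excludes zero in 66-77% of simulated trials. An ordinary session-level interval for the difference does so in 68-80%. Pairing shows no power gain here.

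**The case against.** The strongest reply is that alarms are an additional measure (1.19, 4.4), that 1.18 plans no powered secondary performance measures, and that describing such a measure in 15-20 subjects is defensible. Each alarm is also related to the venous needle by the clinician, and inappropriate footplate opening can occur only with the V Needle. Counts with that attribution can show whether, and how often, false alarms were ascribed to the device.

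Much of this stands. A reader might infer that the plan has no analysis at all that bears on the aim, or that exposure time is missing. The documents support neither: the descriptive summary can show occurrence, and achieved treatment time is recorded at every session. A reader might also expect a gain in power from pairing, which Step 4 does not show. A session-level interval for the difference kept its false-excess rate at 0.7-3.6% with no true difference, because ignoring the pairing makes it conservative. That interval is not in the plan either.

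Another tempting inference is that changes to machine alarm limits could hide V Needle alarms. The documents do not discuss alarm limits, and the form's listed contents are introduced by "Therapy Assessment Form, including the following", so the list need not be complete. Excluding sessions in which limits were changed would moreover condition on the outcome.

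What does not stand is that attribution replaces a contrast. The clinicians are unblinded (7.3), and the footplate limb of the false-alarm definition cannot apply to control sessions.

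**Conclusion.** The concern holds as a gap in the specified analysis. The data needed to estimate an excess of false alarms over control are collected, but no contrast, interval or denominator is prespecified, and the default summary ignores both the pairing and the clustering. The case for change rests on validity and prespecification, with no claim of added power.

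The 62-86% coverage depends on assumed rates of 0.3 to 2.0 alarms per session and between-subject variance of 0.5 to 1; with no between-subject variation, coverage is nominal. It describes the interval for the V Needle rate alone. The ±7 to ±15 points depend on assumed shares of 5-30%. Because control sessions always come first, any V Needle minus control difference, paired or not, is confounded with period, and no analysis of this design removes that.

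**What to change.** Add one paragraph to 10.3:

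- For total blood alarms and for false blood alarms separately, compute each subject's rate under each needle as alarms divided by achieved treatment hours.
- Report the mean within-subject difference (V Needle minus control) with a 95% interval based on subjects, and the number of subjects contributing to it.
- Report the share of sessions with at least one false alarm, by needle.
- Label the comparison unpowered and imprecise with 15-20 subjects.
- State that control sessions precede V Needle sessions, so the difference is confounded with period.

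Reporting total alarms alongside false alarms matters because the total does not depend on the device-specific limb of the false-alarm definition. Section 10.4.1 should list this analysis as a second exception to session-level presentation.

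The cost is a paragraph of text and a short calculation. It needs no extra subjects, sessions, procedures or case report form fields.

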1.2 STUDY TITLE

Confirmatory Study to Assess the V Needle in End-Stage Renal Disease Patients during in-clinic hemodialysis: **Clinic-SAVER Study**

1.3 STUDY DESCRIPTION:

This study is a prospective, multi-center, single-arm study with subjects acting as their own control designed to confirm the safety, performance, and usability of the V Needle, a new safety needle for use during in-clinic hemodialysis that is designed to automatically generate a partial occlusion of the internal fluid path and trigger the hemodialysis machine to alarm and shut off if a complete dislodgement of the venous needle from the arm inadvertently occurs.

1.4 STUDY OBJECTIVES

The study is designed to confirm the safety, performance, and usability of the Hemotek V Needle A.V. Fistula Set for temporary cannulation for hemodialysis in the treatment of end-stage renal disease patients in the clinical setting.

1.5 CLINICAL PHASE

This study is a confirmatory study designed to provide clinical evidence for use in obtaining marketing clearance, i.e. 510(k) clearance, for the Hemotek device.

1.6 INDICATIONS FOR USE

The Hemotek V Needle A.V. Fistula Set is intended for temporary cannulation to vascular access for extracorporeal blood treatment for hemodialysis. This device is intended for single use only. The anti-needlestick safety feature aids in prevention of needle stick injuries when removing and discarding the needle after dialysis. The device also has an integrated safety mechanism that is designed to automatically generate a partial occlusion of the internal fluid path and trigger the hemodialysis machine to alarm and shut off if a complete dislodgement of the venous needle from the arm inadvertently occurs.

1.7 STUDY DEVICE

The Hemotek V Needle A.V. Fistula Set is a set that includes a needle used to access the vasculature during hemodialysis. The V Needle incorporates both a detection system that is designed to detect when the venous needle becomes completely dislodged from the patient's arm

Hemotek Medical Inc. Confidential

and an internal mechanism that is designed to occlude the flow of blood through the needle in the dislodged state. The induced flow occlusion is designed to generate a change in the venous line pressure such that the hemodialysis machine will automatically alarm and halt further pumping. The V Needle used in this study will have a sharp cannula tip with an anti-stick needle guard.

1.8 STUDY RATIONALE

In patients undergoing hemodialysis for the treatment of end-stage renal disease, Venous Needle Dislodgement (VND) is a rare, but potentially fatal situation in which the needle delivering a patient's blood back to the body after filtration by a dialysis machine becomes inadvertently disconnected from the patient. The use of the V Needle as a venous needle return is designed to significantly reduce patient risk from exsanguination-related injury or death. This clinical study will serve to confirm safety, performance, and usability of the device during appropriate hemodialysis therapy. During this study, the safety and performance of the V Needle during delivery of appropriate hemodialysis therapy will be tested. The study will also assess the number of false blood alarms observed under normal operating conditions and the V Needle's usability. V Needle rates of adverse events and ability to complete the hemodialysis session will be compared to the rates recorded using standard available needle sets during hemodialysis sessions prior to the use of the Hemotek V Needle.

1.9 STUDY POPULATION

Adult men and women with end-stage renal disease undergoing chronic hemodialysis with a mature AV fistula or graft in the arm.

1.10 CLINICAL SITES

Between 2 and 4 centers

1.11 NUMBER OF SUBJECTS

Between 15 and 20 subjects (at least 87 test sessions required)

1.12 STUDY DURATION

The study will be conducted over a maximum of nine (9) dialysis sessions (first three (3) are controls) for each patient. Typically, a patient will have three sessions in one week so that the study will last three (3) weeks per patient. Each session usually lasts around three hours. Any adverse events that are reported after the study session (e.g., a hematoma in the days following the session) will also be catalogued and reported. Adverse events will be recorded up until the next dialysis treatment or for one week following the last session if no additional sessions are planned.

1.13 INCLUSION CRITERIA

1. Subjects with end-stage renal disease receiving chronic hemodialysis in a clinical setting.
2. Subjects must be able to receive hemodialysis with the Hemotek 15-gauge, 1 inch length V Needle, with 12 inch tubing.
3. Age greater than 18 years old at screening.
4. Vascular access via a mature arteriovenous (AV) fistula or graft in the arm and determined to be adequate for a chronic hemodialysis therapy.
5. AV fistula has already been demonstrated to adequately permit one or more hemodialysis sessions.
6. Subject prescribed blood flow rates between 200 ml/min and 450 ml/min
7. In women with child-bearing potential, negative urine or serum pregnancy test at Screening.
8. Subject able to communicate effectively with investigative staff, competent and willing to give written informed consent, and able to comply with entire study procedures.
9. Hemoglobin ≥ 9 g/dL (consistent with KDOQI guidelines)
10. Normal platelet count ($\geq 150,000$ /mm³)
11. International Normalized Ratio (INR) ≤ 1.5

